5.5 Blood/serum biomarker analysis

The following serum biomarkers will be measured at baseline (before BTG treatment) and at several time points afterwards (i.e pre-treatment (visit 2), Day 1 after treatment (visit 3), pre-surgery (visit 4) and end of study (visit 6):

- Levels of blood biomarkers (cytokines, chemokines and growth factors relevant to cancer and inflammation).
- Levels of serum alpha-fetoprotein (AFP) in patients with HCC.
- Levels of serum CEA, CA19-9 and CA125 in patients with mCRC.

Time-concentration plots for each biomarker will be obtained for each patient. Each plot would be indicated as to whether the patient had HCC or mCRC.

Changes in levels (last recorded value minus the baseline value, for each patient) summarized as scatter plots, with mean/median and range of the change.

Non-parametric tests to be used for biomarkers that appear to show large changes.

6. Tumour pathology after surgery (of the resected tissue)

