# 1. SCHEMA

# 2. SCHEDULE OF VISITS

Study Visit	Visit 0	Visit 1	Visit 2	Visit 3	Visit 4 	Visit 5	Visit 6
	Screening	Baseline	Treatment Day				End of Study

Assessment	Up to 7 days before registration	Up to 7 days before treatment and following registration	Pre-treatment	Posttreatment	Day 1 after treatment	Up to 3 days prior to surgical resection	Surgical resection (7 to 21 days after treatment)	28-32 days postsurgery
Informed Consent	X							
Patient Demographics	X							
Medical and Prior Treatment History	X							
Eligibility Assessment (Inclusion/Exclusion Criteria)	X							
Child Pugh Assessment (HCC patients only)	X							
Physical Examination	X	X 				X		X
Vital Signs	X	X 	X	X	X	X	X	X
WHO Performance Status	X	X 				X		X
Concomitant Medications	X	X	X	X	X	X	X	X
Assessment of Adverse Events	X	X	X	X	X	X	X	X
Biochemistry	X	X 			X	X		X
Haematology	X	X 2			X	X		X
Coagulation Tests	X	X 2				X		X
12-Lead ECG	X	X 2	X	X		X		X
Serum Pregnancy Test 	X	X 2						
Liver MRI, Incorporating DCE-MRI		X	X 			X		
CT scan chest, abdomen, liver, pelvis, incorporating perfusion CT of liver		X	X 			X		
4D CT scan liver					X			
Blood Biomarker Analysis		X	X		X	X		X
Serum Tumour Markers (AFP for HCC patients; CEA, CA19-9, CA125 for mCRC patients)		X	X			X		

Study Visit	Visit 0	Visit 1	Visit 2		Visit 3	Visit 4 	Visit 5	Visit 6
	Screening	Baseline	Treatment Day					End of Study
Assessment	Up to 7 days before registration	Up to 7 days before treatment and following registration	Pre-treatment	Posttreatment	Day 1 after treatment	Up to 3 days prior to surgical resection	Surgical resection (7 to 21 days after treatment)	28-32 days postsurgery
Vandetanib and N-desmethyl metabolite plasma sampling (0 min, 2hr ( $\pm$ 15 mins), 4hr ( $\pm$ 15 mins), 24h ( $\pm$ 1 hour), and up to hospital discharge  ) in addition to Visits 4 and 6			X	X	X	X		X
Vandetanib and N-desmethyl metabolite tissue sampling, histopathological and biomarker analysis							X	

1. For women of child-bearing potential. A negative pregnancy test must be obtained prior to treatment
2. Do not need to be repeated if screening assessments performed within 7 days prior to treatment
3. May be performed the day before treatment
4. Optional one additional plasma sample can be taken after 36 hours and up to time of hospital discharge

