#### Pre-treatment Assessments

The following scans will be performed within a day prior to administration of BTG-002814:

- Liver MRI, incorporating DCE-MRI, as described in section 7.3.11
- CT scan of chest, abdomen & pelvis, incorporating perfusion CT of liver, as described in section 7.3.11

The following assessments and procedures will be performed on the day of treatment prior to administration of BTG-002814:

- Vital signs will be taken, as described in section 7.3.5
- Record any concomitant medications, as described in section 7.3.20
- Record any adverse events, as described in section 7.3.21
- A 12-lead ECG will be taken, as described in section 7.3.12
- Blood sample for biomarkers, as described in section 7.3.13
- Blood sample for serum tumour markers, as described in section 7.3.10
- Blood sample for vandetanib and metabolite analysis, as described in section 7.3.14

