### 7.2.4. Visit 3 (Day 1 after treatment)

The following assessments and procedures will be performed:

- Vital signs will be taken, as described in section 7.3.5
- Record any concomitant medications, as described in section 7.3.20
- Record any adverse events, as described in section 7.3.21

- 
- 

- Blood samples for biochemistry and haematology, as described in section 7.3.8
- 4D CT scan of liver will be performed, as described in section 7.3.11
- Blood sample for biomarkers, as described in section 7.3.13
- Blood sample for vandetanib and metabolite analysis, as described in section 7.3.14

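### SAP 5.5 gives the tumour markers more visits than the Protocol samples, and its change rule lets a patient without a Visit 4 sample contribute a purely pre-treatment difference

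*SAP*

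**What the plan says.** SAP 5.5 opens with one sentence on sampling times. It names a baseline before treatment and then further samples "at several time points afterwards (i.e pre-treatment (visit 2), Day 1 after treatment (visit 3), pre-surgery (visit 4) and end of study (visit 6"). Three bullets follow under that sentence: the panel of cytokines, chemokines and growth factors; "Levels of serum alpha-fetoprotein (AFP) in patients with HCC"; and "Levels of serum CEA, CA19-9 and CA125 in patients with mCRC". The section then defines the summary measure: "Changes in levels (last recorded value minus the baseline value, for each patient"), to be shown as scatter plots with mean or median and range. Non-parametric tests are reserved for markers whose changes look large. The section does not say which visit is baseline.

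The Protocol's Schedule of Visits keeps the two kinds of marker in separate rows. The row "Serum Tumour Markers (AFP for HCC patients; CEA, CA19-9, CA125 for mCRC patients") is marked at Visit 1, Visit 2 pre-treatment and Visit 4 only. The visit-by-visit lists in Protocol 7.2 agree with it. At Visit 2 the line "Blood sample for serum tumour markers, as described in section 7.3.10" stands under the introduction "The following assessments and procedures will be performed on the day of treatment prior to administration of BTG-002814". At Visit 3 the only marker line is "Blood sample for biomarkers, as described in section 7.3.13", which refers to the cytokine-type panel; the same holds at Visit 6/Early Withdrawal (7.2.7).

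**The concern.** The SAP's visit list fits the blood-biomarker panel but has also been applied to the tumour markers, which follow a shorter schedule. On its own, this would only leave empty cells at Visits 3 and 6. It matters more in combination with the change rule. Once Visits 3 and 6 drop out, a tumour-marker change depends on one post-treatment sample. The rule does not say what to do when that sample is missing, and its literal reading falls back to a sample taken before treatment.

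At stake is whether each plotted and summarised tumour-marker change describes what happened after BTG-002814. The same changes also decide which markers appear to have moved enough to be tested.

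**Working it through.** No figure in the plan needs reproducing. The check sets the two documents side by side and then applies the change rule to each pattern of available samples.

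**Step 1: visits.** Baseline is read as Visit 1, because SAP 5.5 lists Visit 2 separately after it.

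| Visit | Timing | SAP 5.5, all markers | Protocol, blood biomarkers | Protocol, tumour markers |
|---|---|---|---|---|
| 1 | before treatment | yes (baseline) | yes | yes |
| 2 | before treatment, same day | yes | yes | yes |
| 3 | day after treatment | yes | yes | **no** |
| 4 | after treatment, before surgery | yes | yes | yes |
| 6 | after surgery | yes | yes | **no** |

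For the blood-biomarker panel the documents agree at all five visits. For the tumour markers, the SAP lists 5 time points against 3 planned samples. The surplus is Visits 3 and 6, which are two of the SAP's three post-treatment time points. That leaves Visit 4 alone after treatment.

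**Step 2: the change rule, with Visit 1 present.**

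| Tumour-marker samples after Visit 1 | Last recorded | Change |
|---|---|---|
| Visits 2 and 4 | Visit 4 | Visit 4 − Visit 1 |
| Visit 4 only | Visit 4 | Visit 4 − Visit 1 |
| Visit 2 only | Visit 2 | Visit 2 − Visit 1, wholly pre-treatment |
| none | no later value | no change available |

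Only the third row goes wrong. If baseline were instead Visit 2, a patient in that row would get Visit 2 − Visit 2 = 0, which is equally uninformative about treatment. For the blood-biomarker panel, the same fault needs Visits 3, 4 and 6 all to be missing.

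**Step 3: does another rule prevent it?**
- Protocol 5.5 asks for Visit 6 assessments in patients who withdraw early, but that list has no tumour-marker draw.
- Protocol 9.2.1 analyses every treated patient, so a patient without Visit 4 stays in, even if replaced.
- SAP section 1 rules out imputation, but a Visit 2 result is a recorded value, so that rule does not exclude it.

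**Step 4: size.** The target is 6 patients per disease, and each tumour marker belongs to one disease. One affected patient is 1/6 = 17% of that group's changes. The documents give no rate of missing Visit 4, so the rates below are assumptions. Patients are taken as independent, and the probability of at least one affected among n is 1 − (1 − p)^n.

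| Assumed p | n = 6 (one disease) | n = 12 (whole study) |
|---|---|---|
| 5% | 1 − 0.95^6 = 0.27 | 1 − 0.95^12 = 0.46 |
| 10% | 1 − 0.90^6 = 0.47 | 1 − 0.90^12 = 0.72 |
| 20% | 1 − 0.80^6 = 0.74 | 1 − 0.80^12 = 0.93 |

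**The case against.** The strongest reply is that this is an edge case that would be noticed. With Visit 4 present, the rule already gives Visit 4 minus baseline, which is the quantity wanted. SAP 5.5 also calls for a plot over time for each marker in each patient, and SAP section 1 has missing data indicated in the tables. With about 12 patients, a curve ending at Visit 2 would be plain to see. The analysis is descriptive, the study is not powered (Protocol 9.1), and these markers are neither co-primary nor secondary endpoints in the Protocol. All of this stands and keeps the point small. It does not remove it: a visible plot does not alter what the written rule puts into the mean, median and range.

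Four stronger readings are tempting, and the documents do not support them:

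- A reader might infer that the SAP treats Visit 2 as a post-treatment time point. The word for later samples most naturally means after baseline, the SAP itself labels Visit 2 pre-treatment, and SAP 5.4 classes Visits 1 and 2 as pre-treatment for imaging. The fault is only that Visit 2 remains eligible as the last recorded value.
- A reader might infer that the summary is pulled toward zero. That needs both a real treatment effect and no drift between Visits 1 and 2, and neither is shown. One value in six may also hardly move a median.
- A reader might infer that listing Visit 6 brings in routine post-operative tumour markers. Neither document provides for collecting them, and Protocol 7.3.10 ties these tests to the Schedule of Visits.
- A reader might infer that Visits 1 and 2 ought to be averaged as baseline. That is a preference resting on an assumed variance structure. A single pre-treatment baseline is conventional.

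**Conclusion.** The point holds as a minor one. The visit mismatch for AFP, CEA, CA19-9 and CA125 is exact: Visits 3 and 6 are in SAP 5.5 but not in the Protocol. The consequence is conditional. It arises only for a treated patient who has a Visit 2 value and no Visit 4 value, and then that patient's change is wholly pre-treatment. Patients with a Visit 4 sample are unaffected, and the visit list for the blood-biomarker panel is correct.

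The 17% describes one affected patient in a group of six; it is not a forecast. The probabilities rest on assumed rates of 5% to 20% and on independence between patients. No co-primary result depends on this analysis.

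**What to change.** Amend SAP 5.5 as follows:

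1. List the tumour markers separately, at Visits 1, 2 and 4 only, and keep the existing list for the blood-biomarker panel.
2. Name the baseline visit, either Visit 1 or the pre-dose Visit 2 sample, and exclude pre-treatment samples from the last recorded value.
3. Define tumour-marker change as the last post-treatment, pre-surgery (Visit 4) value minus baseline. Both the Schedule of Visits and Protocol 7.2.5 have Visit 4 repeated when surgery is delayed by more than 7 days, so state that the latest such sample counts.
4. Report the change as missing when there is no post-treatment sample.

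The cost is SAP wording only, with no new samples, visits or Protocol amendment. Averaging Visits 1 and 2 is optional and is not part of this correction.

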#### 7.2.2. Visit 1: Baseline Visit (up to 7 days before treatment)

Following fulfilment of the inclusion and exclusion criteria and registration of the patient, the following assessments and procedures are required to be done within 7 days prior to treatment with BTG-002814:

- Liver MRI, incorporating Dynamic Contrast Enhanced MRI (DCE-MRI), as described in section 7.3.11
- CT scan of chest, abdomen & pelvis, incorporating perfusion CT of liver, as described in section 7.3.11
- Blood sample for biomarkers, as described in section 7.3.13
- Blood sample for serum tumour markers, as described in section 7.3.10
- Record any concomitant medications, as described in section 7.3.20
- Adverse events will be recorded and assessed as described in section 7.3.21

The following tests and procedures do not need to be repeated if carried out within 7 days prior to treatment with BTG-002814 as part of screening work up:

- 
- 

Physical examination will be conducted, as described in section 7.3.4

Vital signs will be taken, as described in section 7.3.5

- Performance status will be assessed, as described in section 7.3.6
- Blood samples for biochemistry, haematology and coagulation, as described in section 7.3.8
- A 12-lead ECG will be done as described in section 7.3.12
- Blood sample for serum pregnancy test for all patients of child-bearing potential, as described in section 7.3.9

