### 7.2.7. Visit 6 End of Study/Early Withdrawal (28-32 days postsurgery)

Patients complete the study 28-32 days following the day of surgical resection. The following assessments and procedures will be performed for those patients who complete the study or those who withdraw early.

- Physical examination will be conducted, as described in section 7.3.4
- Vital signs will be taken, as described in section 7.3.5
- Performance status will be assessed, as described in section 7.3.6
- Record any concomitant medications, as described in section 7.3.20

- 
- 

- Record any adverse events, as described in section 7.3.21. Any AEs related to BTG-002814 continuing at this visit should be recorded as 'ongoing' in the patient's medical notes and CRFs.
- Blood samples for biochemistry, haematology and coagulation, as described in section 7.3.8
  - A 12-lead ECG will be taken, as described in section 7.3.12
  - Blood sample for biomarkers, as described in section 7.3.13
  - Blood sample for vandetanib and metabolite analysis, as described in section 7.3.14
- As appropriate, record the date and reason for study completion as listed in section 5.4 □  
As appropriate, record the date and reason for study withdrawal as listed in section 5.5

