### 7.3.13. Blood Biomarkers

Approximately 4 mL of blood will be collected at the timepoints shown in the schedule of visits for the measurement of blood biomarkers. The analysis will be performed by the ECMC GCLP Laboratory at UCL Cancer Institute.

Blood biomarkers will be measured to indicate the activity of the investigational treatment on the target cancer, specifically cytokines, chemokines and growth factors relevant to cancer and inflammation.

Detailed information on sample handling, storage and shipping are provided in the Laboratory Manual.

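### For the cytokine, chemokine and growth-factor panel, the only numeric change in SAP 5.5 ends after liver resection, and tests are chosen by the size of the observed change

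*SAP*

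**What the plan says.** SAP 5.5 covers two groups of markers: the panel of cytokines, chemokines and growth factors, and the disease-specific tumour markers (AFP in HCC; CEA, CA19-9 and CA125 in mCRC). For both it names a baseline, a pre-treatment sample at Visit 2, and then "Day 1 after treatment (visit 3), pre-surgery (visit 4) and end of study (visit 6").

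It plans three things:

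- a concentration-time plot per marker and patient;
- a change summary, defined as "Changes in levels (last recorded value minus the baseline value, for each patient"), shown as scatter plots with mean or median and range;
- tests, under this rule: "Non-parametric tests to be used for biomarkers that appear to show large changes".

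It names no test, significance level, threshold for a large change, marker list or multiplicity rule.

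Protocol 7.3.13 gives the purpose of the panel: "Blood biomarkers will be measured to indicate the activity of the investigational treatment on the target cancer". Protocol 7.2.7 includes the panel at the last visit ("Blood sample for biomarkers, as described in section 7.3.13") and fixes that visit's timing: "Patients complete the study 28-32 days following the day of surgical resection". Protocol 9.4.6 plans descriptive summaries of levels and changes, and no tests.

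**The concern.** Surgery lies between treatment and the last panel sample. Resection removes the tumour, and several weeks of recovery follow before Visit 6. A single-arm study has no control group to separate these influences from the effect of the beads. A reader who takes the mean change as a sign of treatment activity, which is the stated purpose of the panel, would be reading a number that also reflects the operation.

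The end point is also not fixed across patients. Protocol 5.5 asks that patients who withdraw have the Visit 6 assessments beforehand if possible. A treated patient who leaves before surgery would then put a pre-resection value into the same mean or median. The documents give no expected number of such patients.

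The testing rule raises a different problem. If a marker is tested because its change looks large in these patients, the p-value has lost its usual meaning, and the report would show mainly the results that were favoured in advance.

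**Working it through.** The plan states no power, significance level or effect size for these markers, so there is no figure of its own to reproduce. The check uses the visit windows, a comparison of sections, and an illustration under stated assumptions.

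**1. When the last panel value falls.** Inputs: surgery 7-21 days after treatment (Protocol 6.1.4); Visit 6 28-32 days after surgery (Protocol 7.2.7); Visit 4 from 3 days to 1 day before surgery (SAP 4.2.1, consistent with Protocol 7.2.5); panel drawn at Visits 1, 2, 3, 4 and 6 (Protocol 2 and 7.2.2 to 7.2.7).

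- Visit 6, days after treatment: 7 + 28 = 35 to 21 + 32 = 53.
- Post-operative share of the treatment-to-last-sample interval: smallest 28 / (21 + 28) = 28/49 = 57%; largest 32 / (7 + 32) = 32/39 = 82%.
- Visit 4, days after treatment: 7 − 3 = 4 to 21 − 1 = 20.
- Gap from Visit 4 to Visit 6: 1 + 28 = 29 to 3 + 32 = 35 days.

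**2. Comparison within the SAP.** SAP 5.4 measures perfusion change at Visit 4, before surgery. SAP 6.2 takes tumour-size change from baseline to pre-surgery. Only SAP 5.5 lets the change run past the operation, although panel samples at Visits 3 and 4 are already scheduled.

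**3. Baseline.** Visit 1 ("Visit 1: Baseline Visit (up to 7 days before treatment")) and the Visit 2 sample taken before administration are both pre-treatment. SAP 5.5 lists Visit 2 among the later time points, so the value to be subtracted should be named.

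**4. Tumour markers.** The row "Serum Tumour Markers (AFP for HCC patients; CEA, CA19-9, CA125 for mCRC patients") in the protocol schedule is marked at Visits 1, 2 and 4 only. The lists for Visit 3 (7.2.4) and Visit 6 (7.2.7) omit these markers. SAP 5.5 lists both visits for them. On the protocol schedule their last value is the Visit 4 sample, before surgery, so step 1 does not apply to them.

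**5. Effect of choosing tests by observed change.** Assumed, because the documents do not give them: a panel of 10, 20 or 40 markers; no true change in any; Normal changes; 12 patients; the three largest changes tested; exact two-sided signed-rank test, p < 0.05. Without selection the attainable level is 174 of the 2^12 = 4,096 sign patterns, or 4.2%. Share of reported p-values below 0.05:

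| How the largest changes are picked | 10 markers | 20 | 40 |
|---|---|---|---|
| Mean/SD, independent markers | 14% | 27% | 50% |
| Mean/SD, correlation 0.3 | 14% | 26% | 43% |
| Mean/SD, correlation 0.6 | 12% | 20% | 30% |
| Raw mean, independent, equal SDs | 14% | 25% | 40% |
| Median, independent, equal SDs | 12% | 19% | 26% |
| Raw mean, independent, SDs log-normal across markers (log-SD 1.5) | 8% | 10% | 11% |

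Ranking by mean/SD comes close to ranking by the test statistic itself, so the first row is an upper case. With unequal marker scales, raw size of change says less about the p-value and the inflation is much smaller. Adding correlation to the last row would lower it further, so 8% is not a floor.

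**The case against.** The strongest reply is that SAP 5.5 never calls the last-minus-baseline value a treatment effect. Protocol 9.4.6 asks for changes across the whole study, and this is one literal version of that. The exploratory objective is to find markers of likely response, and no change-score estimand is stated. The per-patient plots display Visits 3 and 4. This stands in part: a whole-study change is a legitimate description, and the pre-surgery data are neither lost nor hidden. It does not justify making that change the only numeric summary of markers meant to indicate treatment activity.

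On testing, the panel size, the number tested and the meaning of a large change are all assumed above, and if nothing looks large nothing is tested. That is fair. The direction of the bias follows from the rule, but its size does not.

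A reader might go further in four ways that the documents do not support:

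- That the tumour-marker changes are contaminated by surgery too. On the protocol schedule they end at Visit 4.
- That half of the reported p-values would be false positives. That is the top of the range, with every marker null and 40 independent markers.
- That a change ending at Visit 4 would isolate the treatment effect. Without a control group it is a pre-surgery change and no more.
- That the protocol forbids tests here. Protocol 9.1 calls the analysis mainly descriptive, which leaves room for exploratory tests.

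**Conclusion.** The point holds, with low severity. As written, the panel's only numeric change, and any test on it, ends on Day 35-53 in completers who keep to schedule, with 57% to 82% of the interval after resection. It cannot separate treatment from surgery. These timing figures need only the visit windows.

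The rule for choosing tests makes the p-values unreadable at face value. The 8% to 50% range against 4.2% is an illustration that depends on assumed panel size, number tested, selection rule, marker scales and correlation.

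The tumour-marker visits are a plain mismatch between SAP and protocol. The endpoint is exploratory, the study is unpowered, no decision rule uses these summaries, and the primary endpoints are unaffected.

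**What to change.** In SAP 5.5:

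1. For the panel, report the pre-surgery change: last sample before surgery (Visit 4, or its repeat if surgery is delayed) minus one named pre-treatment baseline. Add the Visit 3 change from the same baseline. Summarise post-resection values separately, classifying samples by date relative to surgery and not by visit number. Label the first quantity a pre-surgery change, not a treatment-related one.
2. Remove the rule that picks tests by observed change. Either describe only, in line with Protocol 9.4.6, or fix the marker list and a paired Wilcoxon signed-rank test before the data are seen, report every result, and either adjust the p-values or label them exploratory and unadjusted.
3. Reconcile the AFP, CEA, CA19-9 and CA125 visits with the protocol schedule.

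For the panel this costs only SAP wording, since the samples are already scheduled. A protocol change is needed only if tumour markers at Visit 3 or Visit 6 are really intended. The downside is that the pre-surgery change reaches only about Day 4-20 after treatment, so later effects would appear only in the post-resection summary. A fixed list without adjustment removes the selection but not the multiplicity.
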